17.0 Safety Assessments and Monitoring

17.1 Definition of an Adverse Event

An AE is any untoward medical occurrence associated with the use of a drug in humans, whether or not considered drug related. An AE can therefore be any unfavorable and unintended sign (including an abnormal laboratory finding), symptom or disease temporally associated with the use of a study drug/study intervention, whether or not related to the study drug/study intervention.

Any laboratory abnormality that is deemed to be clinically significant in the opinion of the investigator will be considered an AE and should be recorded in the eCRF, whether or not it is related to the study drug.

Stable chronic conditions that are present prior to clinical trial enrollment and do not worsen are not considered AEs and will be accounted for in the subject's medical history. The following can be considered AEs:

- An exacerbation of a pre-existing illness
- An increase in frequency or intensity of a pre-existing episodic event or condition
- A condition detected or diagnosed after the initiation of treatment with study medication, even though it may have been present prior to the start of the study
- Continuous persistent disease or symptoms present at Baseline that worsen after signing the informed consent or following the initiation of treatment with study medication

The following are **not** considered AEs:

- Medical or surgical procedures (e.g., surgery, endoscopy, tooth extraction or transfusion); the condition that leads to the procedure is an AE
- Pre-existing disease or conditions present or detected at the start of the study that do not worsen
- Situations where an untoward medical occurrence has not occurred (e.g., hospitalizations for cosmetic surgery or elective surgery or social/convenience admissions)
- The disease being studied, or signs or symptoms associated with the disease, unless more severe than expected for the subject's condition or a worsening of the disease being studied

17.2 Definition of a Serious Adverse Event

A SAE is defined as an AE meeting one of the following outcomes:

- Death
- Life-threatening event

- Inpatient hospitalization or prolongation of existing hospitalization
- Persistent or significant disability/incapacity or substantial disruption of the ability to conduct normal life functions
- Congenital anomaly or birth defect

Any other important medical event that may not result in one of the above outcomes may be considered a SAE when, based upon appropriate medical judgment, the event may jeopardize the participant and may require medical or surgical intervention to prevent one of the outcomes listed above.

A life-threatening AE is any AE that places the subject, in the view of the investigator, at immediate risk of death from the AE as it occurred. It does not include an AE that, had it occurred in a more severe form, might have caused death.

17.3 Events of Clinical Interest

The following are considered events of clinical interest (ECIs), and must be recorded as such on the AE eCRF when the PI becomes aware of the ECI:

- QTc >500 ms or a >60-ms change from Baseline, confirmed by repeat testing
- ALT or AST >8 x ULN, if new compared to Baseline, confirmed by repeat testing
- ALT or AST >5 x ULN for more than 2 weeks and if new compared to Baseline, confirmed by repeat testing
- ALT or AST >3 x ULN and either total bilirubin >2 x ULN or INR >1.5 and if new compared to Baseline, confirmed by repeat testing
- ALT or AST >3 x ULN, confirmed by repeat testing, with the appearance of fatigue, nausea, vomiting, right upper quadrant pain or tenderness, fever, rash, and/or eosinophilia (>5%)]

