In Phase 1 studies, oral SCY-078 has been generally safe and well tolerated following single oral doses of up to 1600 mg and multiple oral doses of up to 800 mg for 28 consecutive days. In Phase 2 and 3 studies, SCY-078 was also generally safe and well tolerated. The dose regimens have included a loading dose of up to 1500 mg (750 mg BID) on Days 1 and 2 followed by maintenance doses of 750 mg once daily (QD) for up to 90 days in patients with refractory fungal infections.

Adverse events (AEs) with oral SCY-078 were generally transient and mild to moderate in intensity. The most frequently reported treatment-related AEs were mild to moderate

gastrointestinal (GI) events (diarrhea, nausea, abdominal pain, and vomiting). There appears to be a dose relationship with the frequency and severity of GI AEs. With the exception of transient increases in liver function tests (LFTs) in a few subjects (not clinically significant but notable), no clinically important abnormalities have been noted in routine blood and urine chemistry panels, electrocardiograms (ECGs), and physical examinations including vital signs.

Peak plasma concentrations after oral administration of SCY-078 occur within approximately 4 to 6 hours post-dose. Plasma concentrations decline from C_{max} in an approximately monophasic decline, with a harmonic mean terminal half-life of ~20 hours. Dosing with a high-fat meal increased AUC and C_{max} by ~60%, within the intersubject variability. The mean AUC_{0-∞} and C_{max} appeared, in general, to be dose proportional for doses from 10 mg to 1600 mg. Plasma exposures of SCY-078 were not altered in subjects who were older than 65 years compared to younger subjects or in healthy female subjects compared to healthy male subjects after single oral dose administration.

Additional pre-clinical and clinical information can be found in the Investigator's Brochure (IB).

Drug-Drug Interactions Potential

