12.2 Exclusion Criteria

A subject will be excluded from participation in the study if he or she meets any of the following exclusion criteria:

1. Subject has a fungal disease with central nervous system involvement suspected at Screening.

- 2. Subject is receiving, has received or anticipates to be receiving concomitant medications that are listed in the prohibited medication list (Section 22.1) within the specified washout periods.
- 3. Subject has a Karnofsky score <20.
- 4. Subject is expected to die from a non-infectious cause within 30 days from the day the study ICF is signed.
- 5. Subject is under mechanical ventilation.
- 6. Subject has abnormal liver test parameters: AST or ALT ≥5 x ULN and/or total bilirubin >2.5 x ULN.

Note: Subjects with unconjugated hyperbilirubinemia (< 7mg/dL) with a diagnosis of Gilbert's disease **are not excluded**.

- 7. Subject has a grade II-IV acute or extensive chronic graft-versus-host disease (GvHD).
- 8. Subject has renal failure requiring dialysis.
- 9. Subject has a prolonged QTcF interval (Fridericia's correction: QTc= QT/(RR)^{0.33}) >480 ms for females and prolonged QTcF interval (Fridericia's correction: QTc= QT/(RR)^{0.33})
 >450 ms for males, on the baseline ECG or other abnormalities deemed clinically significant by the investigator that would put the subject at unacceptable risk for participation in the study.
- 10. Subject has any other condition including history of conditions or medications that may increase the risk for QTc prolongation, or laboratory abnormality that, in the judgment of the investigator, would put the subject at unacceptable risk for participation in the study or may interfere with the assessments included in the study.
- 11. Subject has a known hypersensitivity to SCY-078 and/or voriconazole or any of the components of the formulations.
- 12. Subject has participated in any other investigational study (except open-label studies including approved chemotherapy agents) within at least 28 days or 5.5 half-lives of the investigational product (whichever is longer) before signing the ICF.
- 13. Subject has received prior treatment with SCY-078 in a previous trial.
- 14. Subject is an employee of SCYNEXIS, Inc., the investigator or the Contract Research Organization (CRO) involved in the study, or is an immediate family member (partner, offspring, parent, sibling, or sibling's offspring) of an employee involved in the study.

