19.6.2 Safety Analyses

All safety analyses will be conducted using the ITT/safety population; all safety variables will be listed.

The incidence and severity of TEAEs and SAEs and their relationship to treatment will be summarized. AEs will be coded using the Medical Dictionary for Regulatory Activities (MedDRA) Version 19.1 or higher and presented by system organ class and preferred term.

Early discontinuation of study drug treatment will be presented and will include the reasons for and timing of such discontinuations.

Prior and concomitant medications will be summarized; medications will be classified based on the World Health Organization's Drug Dictionary terminology.

Abnormal physical examinations will be listed. Laboratory evaluations will be summarized as observed values and changes from Baseline; shifts with respect to the laboratory reference range will be summarized. Events of clinical interest will be summarized.

Vital signs and ECG evaluations will be summarized as observed values and changes from Baseline.

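### The ALT/AST-with-symptoms event of clinical interest has no baseline condition, so an unchanged eligible elevation plus a new symptom counts as an event

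*Protocol*

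**What the plan says.** Protocol 17.3 opens with a mandatory instruction: an ECI "must be recorded as such on the AE eCRF when the PI becomes aware of the ECI". Four of its bullets rest on ALT or AST. Three tie the finding to Baseline:

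- the highest threshold: "ALT or AST >8 x ULN, if new compared to Baseline, confirmed by repeat testing"
- a lower threshold, for values over 5 x ULN that persist past 2 weeks, under the same condition
- the rule above 3 x ULN with raised bilirubin or INR, which ends "INR >1.5 and if new compared to Baseline, confirmed by repeat testing"

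The last does not: "ALT or AST >3 x ULN, confirmed by repeat testing, with the appearance of fatigue, nausea, vomiting", continuing with right upper quadrant symptoms, fever, rash and eosinophilia. Here the word for newness attaches to the symptom, not to the enzyme value.

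The entry limit is exclusion 6 in Protocol 12.2, repeated in SAP 3.5.2: "Subject has abnormal liver test parameters: AST or ALT ≥5 x ULN and/or total bilirubin >2.5 x ULN".

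For analysis, Protocol 19.6.2 says "Events of clinical interest will be summarized". SAP 6.1 presents summaries by treatment group unless stated otherwise. SAP 10.3 and 10.4 list the adverse event and laboratory outputs; none is an ECI table. SAP 12 declares no departures from the analyses planned in the protocol.

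**The concern.** An on-treatment event defined by a threshold that lies below the entry limit needs a baseline condition. Without one, a subject can meet the laboratory half of the definition on the day of enrolment and needs only a symptom to complete it.

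The symptoms that complete it are not specific to the liver in this trial. Protocol 8.1 names as the most frequent treatment-related events of SCY-078 mild to moderate "gastrointestinal (GI) events (diarrhea, nausea, abdominal pain, and vomiting", with an apparent dose relationship. Protocol 15.11 lists fever among the signs of the fungal disease itself. Repeat testing does not screen these cases out, because a stable elevation repeats.

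At stake is the meaning of the ECI summary in a trial whose primary objective is safety. A reader would take a count under a transaminase rule as liver change, while some of it could be liver status at entry combined with poor gastrointestinal tolerance or symptoms of the infection.

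**Working it through.** The plan gives no figure to reproduce. The check compares the eligible baseline range with each rule.

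**Inputs.** Eligible at Baseline: ALT and AST below 5 x ULN, total bilirubin up to 2.5 x ULN, no INR limit in exclusion 6 (Protocol 12.2). Thresholds from Protocol 17.3. Arm size about 11 (SAP 3.4).

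**Step 1: can an eligible baseline value already satisfy the laboratory part?**

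| Rule in 17.3 | Overlap with eligible baseline | Baseline condition | Overlap closed? |
|---|---|---|---|
| >8 x ULN | none | yes | not needed at entry |
| >5 x ULN for more than 2 weeks | none | yes | not needed at entry |
| >3 x ULN with bilirubin >2 x ULN or INR >1.5 | ALT/AST >3 to <5, with bilirubin >2 to 2.5 or INR >1.5 | yes | yes |
| >3 x ULN with symptoms | ALT/AST >3 to <5 | none | **no** |

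The condition is missing from one of the two rules where the overlap makes it necessary.

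**Step 2: apply the rules literally** (hypothetical records; bilirubin and INR normal; the repeat test confirms the value).

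- Record A: ALT 4.0 at Baseline, 4.0 on Day 7, nausea from Day 5. Change 4.0 - 4.0 = 0. Only the last rule is met: an ECI.
- Record B: ALT 4.5 at Baseline, 3.2 on Day 14, new fever. Change 3.2 - 4.5 = -1.3, an improvement. Only the last rule is met: an ECI.
- Record C: ALT 4.0 at Baseline, 7.5 for 10 days, new right upper quadrant pain. 7.5 is below 8, and 10 days is less than 2 weeks. Only the last rule is met: an ECI, and a true worsening.

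The last rule therefore catches A and B, which show no deterioration, and is also the only rule that catches C.

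**Step 3: weight of one event.** 1/11 = 0.091, or 9 percentage points of an arm.

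**Step 4: illustration only.** The share of subjects entering above 3 x ULN and the symptom rates are not in the documents. Assume 5-20% enter above 3 and below 5 x ULN and stay above 3 without a rise, and that a listed symptom appears in 30-60% on SCY-078 and 20-30% on placebo. Expected events without liver change per arm = 11 x share x symptom rate:

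- SCY-078: 11 x 0.05 x 0.30 = 0.17 to 11 x 0.20 x 0.60 = 1.3
- Placebo: 11 x 0.05 x 0.20 = 0.11 to 11 x 0.20 x 0.30 = 0.66
- A middle case: 11 x 0.10 x 0.50 = 0.55 against 11 x 0.10 x 0.30 = 0.33, a difference of 0.22 subjects, or 0.22/11 = 2 percentage points

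The two symptom ranges meet at 30%, where the expected difference is zero.

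**The case against.** The strongest reply is that 17.3 works inside 17.1. ECIs go on the adverse event form, and 17.1 says that a pre-existing condition that does not worsen is not an adverse event, nor are symptoms of the disease under study unless they exceed what is expected. On that reading Record B might never be entered. This shows ambiguity but does not settle it. 17.3 sets its own criteria with a mandatory recording instruction and does not refer to 17.1, the new nausea in Record A is an adverse event in its own right, and the neighbouring bullets state the baseline condition expressly.

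A second reply is that the rule is meant as a sensitive flag. The documents do not say so, and the other rule at 3 x ULN, which adds bilirubin or INR, does carry the condition. Record C does show that sensitivity has value: if the missing clause were simply inserted and read as requiring the crossing of 3 x ULN to be new, that worsening would no longer be flagged. This part of the objection stands and shapes the fix.

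A third reply is that little depends on the count. Largely true. ECIs are not in the primary endpoint (Protocol 10.1, SAP 4.1), the SAP specifies no ECI table, and no dosing or discontinuation rule in the documents refers to ECI status. The laboratory changes from Baseline in SAP 10.4 would help a reader to check an apparent signal. The ECI summary in Protocol 19.6.2 is nevertheless still promised.

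A reader might go further and infer that the rule will produce a false liver signal against SCY-078. The documents do not support that. Protocol 8.1 reports gastrointestinal events with SCY-078 but gives no comparison with voriconazole plus placebo in this population, and nothing states how many subjects entered above 3 x ULN.

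**Conclusion.** The inconsistency is in the text and needs no assumption: of the four ALT/AST rules in 17.3, only the last lacks a baseline condition, while exclusion 6 admits values above 3 and below 5 x ULN. As written, unchanged or improving transaminases still above 3 x ULN, with a new listed symptom, must be recorded as an ECI.

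The consequence is confined to ECI recording and to any ECI summary made under Protocol 19.6.2, which can mix liver change with entry status and tolerability. The number of subjects affected cannot be computed from the documents and may be zero. Neither the existence nor the direction of an imbalance between arms is established; a lean towards SCY-078 is plausible but rests on assumed symptom rates. What makes the point worth settling is the arm size, where one such event is 9 percentage points, and the small cost of settling it.

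**What to change.** **Protocol 17.3.** Reconcile the last bullet with the other three ALT/AST bullets and with exclusion 6, saying whether the missing baseline condition is intended. Leave site recording of these events as it is, so that a worsening such as Record C is not lost. Enrolment has stopped at 22 subjects (SAP 11 and 12), so the working correction belongs in the SAP.

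**SAP 10.3.** Add the ECI summary that the protocol promises, by treatment group, and split events under the last rule:

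- (a) Baseline ALT/AST at or below 3 x ULN, or an on-treatment value above Baseline: counted as hepatic ECIs.
- (b) Baseline above 3 x ULN with no rise from Baseline: listed separately, with Baseline and on-treatment values.

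Compare each enzyme with its own Baseline value. Say that the value that triggered the event is used even when it is a repeat or unscheduled test, because SAP 6.1 otherwise keeps such tests out of summaries. Under this split Records A and B move to (b) and Record C stays in (a).

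**Cost.** One derivation and one listing. Baseline ALT and AST are already collected, and Baseline is defined in SAP 6.2. The headline ECI count may fall, but every event remains visible. One limit remains: with no margin on a rise, a move from 4.0 to 4.1 x ULN with nausea still falls in (a). The documents offer no basis for choosing a margin, and printing both values lets a reader judge.

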17.4 Overdose

This refers to the administration of a quantity of a medicinal product given per administration or cumulatively, which is above the maximum recommended dose according to the authorized product information.

An overdose can occur if a subject has taken, accidentally or intentionally, a drug administered in a dose exceeding the protocol-specified dose. An overdose must be reported within 24 hours of the site becoming aware of the overdose if such overdose occurs with an associated SAE. If an overdose occurs without an associated SAE, the overdose must be reported within 5 working days and documented in the subject medical record.

17.5 Pregnancy

Female subjects who become pregnant should be immediately discontinued from the study and followed up to determine the outcome of the pregnancy. The pregnancy must be reported to the Sponsor within 24 hours of the site becoming aware of the pregnancy. If the pregnancy ends for any reason before the anticipated date, the investigator should notify the Sponsor. At the completion of the pregnancy, the investigator will document the outcome of the pregnancy. If the outcome of the pregnancy meets the criteria for immediate classification as an SAE (i.e., postpartum complication, spontaneous abortion, stillbirth, neonatal death or congenital anomaly), the investigator should follow the procedures for reporting an SAE.

17.6 Unexpected Adverse Event

An AE is considered "unexpected" if it is not listed in the IB or is of greater specificity or severity than those that have been observed with the particular study drug being tested. For example, under this definition, hepatic necrosis would be unexpected (by virtue of greater severity) if the IB referred only to elevated hepatic enzymes or hepatitis. Similarly, cerebral thromboembolism and cerebral vasculitis would be unexpected (by virtue of greater specificity) if the IB listed only cerebral vascular accidents. "Unexpected," as used in this definition, also refers to AEs that are mentioned in the IB as occurring with a class of drugs or as anticipated from the pharmacological properties of the drug but are not specifically mentioned as occurring with the particular drug under investigation.

17.7 Grading of Adverse Events

The severity (or intensity) of an AE refers to the extent to which it affects the subject's daily activities and will be classified by the investigator as mild, moderate or severe using the following criteria:

- Mild: Awareness of sign or symptom, but easily tolerated. Not likely to require medical attention.
- Moderate: Discomfort enough to cause some interference with daily activity. May require medical intervention.
- Severe: Intense enough to disrupt daily activities. Likely requires medical intervention.

Clarification of the difference in meaning between "severe" and "serious"

The term "severe" is often used to describe the intensity (severity) of a specific event (as in mild, moderate or severe myocardial infarction); the event itself, however, may be of relatively minor medical significance (such as severe headache). This is not the same as "serious", which is based on the outcome or action criteria usually associated with events that pose a threat to life or functioning. Seriousness (not severity) serves as a guide for defining regulatory reporting obligations.

17.8 Causality Assessment

The investigator will assess causality (i.e., whether there is a reasonable possibility that the study drug caused the event) for all AEs and SAEs. The relationship will be characterized using the following classification:

- Related: The temporal relationship of the AE with the study drug makes causality possible and cannot be due to another cause such as other drugs, a surgical intervention or an underlying disease.
- Not related: The temporal relationship of the AE with the study drug makes causality improbable and can be due to another cause such as other drugs, a surgical intervention or an underlying disease.

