10.0 Study Endpoints

10.1 Primary Endpoints

• Frequency of treatment-emergent adverse events (TEAEs), drug-related adverse events (AEs), discontinuations due to AEs and deaths.

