10.3. Adverse Events

Adverse events will be coded into SOCs and PTs using the MedDRA 26.0 .

If the relationship to a study drug is missing then in the summary tables the AE will be classified as related. Similarly, missing severity will be classified as severe in the summary tables.

Treatment-related AEs will be those with relationship to either ibrexafungerp or voriconazole of related.

Summary tables of AEs will be based on treatment emergent adverse events (TEAEs).

A TEAE is defined as any event not present prior to the initiation of the study treatment, or any event already present which worsens either in intensity or frequency following the exposure to the study treatment.

AEs with incomplete start dates will be considered as TEAE if:

- Day and month are missing and the year is equal to or after the year of the first dose date
- Day is missing and the year is after the year of the first dose
- Day is missing and the year is equal to the year of the first dose date and the month is equal to or after the month of the first dose date
- Year is missing
- Complete start date is missing.

For summaries by SOC and PT, a subject will be counted once at the SOC level and once at each PT within the SOC level. For summaries by SOC, PT and maximum severity, a subject will be counted once at the highest severity for which an event occurred at the SOC level and the highest severity for each unique PT within that SOC level. Therefore, subjects may only contribute once to each PT and once to each SOC level.

An overall summary of TEAEs will be provided showing the number and percentage of subjects reporting TEAEs, treatment-related TEAEs, TEAEs with severe severity, TEAEs leading to withdrawal of study treatment, serious TEAEs and treatment-related serious TEAEs, TEAEs leading to Death.

The following TEAE tables will also be provided:

- A summary of TEAEs overall and by SOC and PT
- A summary of treatment-related TEAEs overall and by SOC and PT
- A summary of TEAEs by maximum severity, overall and by SOC and PT
- A summary of TEAEs leading to withdrawal of study treatment, overall and by SOC and PT
- A summary of serious TEAEs, overall and by SOC and PT
- A summary of treatment-related serious TEAEs, overall and by SOC and PT
- A summary of TEAEs leading to Death, overall and by SOC and PT

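### The two causality categories in Protocol 17.8 leave common cases unclassified and contradict that section's own standard, so the drug-related AE count depends on how each investigator resolves the conflict

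*Protocol*

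**What the plan says.** Protocol 17.8 (Causality Assessment) sets the question for every AE and SAE: "whether there is a reasonable possibility that the study drug caused the event". It then gives two categories and no third.

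- *Related*: the timing "makes causality possible and cannot be due to another cause such as other drugs", surgery or underlying disease.
- *Not related*: the timing "makes causality improbable and can be due to another cause such as other drugs, a surgical intervention or an underlying disease".

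Protocol 10.1 defines the primary endpoint as "Frequency of treatment-emergent adverse events (TEAEs), drug-related adverse events (AEs), discontinuations due to AEs and deaths". SAP 4.1 repeats it.

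SAP 10.3 builds tables of treatment-related TEAEs and treatment-related serious TEAEs on this coding. It counts an AE as treatment-related if it is coded related to either ibrexafungerp (SCY-078) or voriconazole. It also has a rule for blanks: "If the relationship to a study drug is missing then in the summary tables the AE will be classified as related".

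**The concern.** Each category joins two conditions with *and*, and the two pairs do not cover all cases. The *Related* category is also much narrower than the question it is meant to answer. A reasonable possibility of drug causation can exist alongside another possible cause, yet *Related* requires that no other cause be possible.

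This matters more here than in most trials:

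- All subjects receive voriconazole, which Protocol 13.3 treats as standard of care and not as the study drug. Another drug is therefore always on board.
- Protocol 12.1 requires hematological disease or transplantation, neutropenia, T-cell immunosuppression or inherited immunodeficiency. Underlying disease is therefore nearly always a candidate cause.
- Liver tests show the problem. Protocol 8.1 reports transient increases with SCY-078, Protocol 15.17 monitors transaminases and bilirubin because of the voriconazole label, and Protocol 17.3 lists transaminase elevations as events of clinical interest. Such an elevation can seldom be shown to have no other possible cause.

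At stake is the comparability of a named primary endpoint component across sites, and possibly its level.

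**Working it through.** The plan states no figure to reproduce. Protocol 19.1 gives no formal sample size calculation, and the point does not depend on one. The check is logical, followed by simple arithmetic on its leverage.

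**Step 1. Cross the two conditions in Protocol 17.8.**

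| Timing | Another cause | Category under 17.8 |
|---|---|---|
| Causality possible | Cannot be | Related |
| Causality possible | Can be | None |
| Causality improbable | Cannot be | None |
| Causality improbable | Can be | Not related |

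Two of the four combinations have no category. The second row is the ordinary ambiguous case in this population.

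**Step 2. Apply the definitions to each drug, as SAP 10.3 presupposes.** Suppose an event could have been caused by either SCY-078 or voriconazole. Read literally, each drug is the other's alternative cause, so the event fails *Related* for both.

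**Step 3. Follow an unclassified event into the SAP tables.**

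- Coded *Not related* to both drugs: not counted.
- Coded *Related* to either drug, following the opening standard of 17.8: counted.
- Left blank: counted as related under SAP 10.3.

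The same event can therefore raise the count or leave it unchanged, and no document says which coding to use.

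**Step 4. Leverage of one subject.** SAP 10.3 reports the number and percentage of subjects with an event. A subject matters here only if the *Related* status turns entirely on unclassified events. One such subject moves the arm's rate by 100/n percentage points.

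- n = 11 (SAP 3.4, as revised): 100/11 = 9.1 points.
- n = 30 (Protocol 11.2, as planned): 100/30 = 3.3 points.

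**Step 5. Illustration with assumed counts that are not in the documents.** Take 2 of 11 subjects with a clearly related AE, plus g further subjects who have only unclassified events.

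| g | All coded Not related | All coded Related or left blank |
|---|---|---|
| 1 | 2/11 = 18.2% | 3/11 = 27.3% |
| 3 | 2/11 = 18.2% | 5/11 = 45.5% |
| 5 | 2/11 = 18.2% | 7/11 = 63.6% |

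The spread shows sensitivity to the coding choice. It does not estimate a bias.

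**The case against.** A reader might infer from the word *cannot* that drug-related AEs are under-counted and that the primary safety result is biased toward no drug effect. The documents do not support that, for these reasons:

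- **The opening standard points the other way.** An investigator who follows it will code ambiguous events *Related*.
- **The SAP rules push the count up.** A blank counts as related, and so does relatedness to either drug. An event firmly attributed to voriconazole still enters the treatment-related tables.
- **Only one primary component is exposed.** TEAEs, discontinuations due to AEs and deaths do not use the causality code. SAP 10.3 also tabulates serious TEAEs, TEAEs leading to withdrawal and TEAEs leading to death regardless of causality.
- **Assessment is double-blind, with one rule for both arms.** Literal coding could shrink a difference between arms, but nothing in the documents shows a between-arm effect.
- **Expedited reporting has a partial safeguard.** Protocol 17.10 leaves the judgement on regulatory submission to the medical monitor or sponsor. Protocol 17.12 sends every SAE to the sponsor within 24 hours, whatever the investigator's causality code.

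All of this stands as a limit on direction and size. It does not repair the definitions. Protocol 17.8 requires a causality judgement for all AEs and SAEs, so a blank is an omission and not a sanctioned answer. The missing-data rule also does nothing for an event placed in *Not related*. If some investigators follow the opening standard and others the category wording, that inconsistency is itself the defect.

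**Conclusion.** Protocol 17.8 is wrong as written: its two categories are not exhaustive, and they conflict with the standard in the same section. This follows from the text alone and is firm. That the gap will be met often is a judgement, based on universal voriconazole use and the eligibility criteria.

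The drug-related AE component and the treatment-related TEAE tables therefore depend on unstated choices. Under-counting is the likely risk if the category wording is applied literally, but neither its direction nor its size can be established from the documents. With about 11 subjects per arm, a handful of such choices could change the reported rate materially, at about 9.1 points per affected subject. The number of affected subjects is unknown.

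The issue should be corrected, but it does not undermine the primary safety assessment as a whole.

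**What to change.** Replace the two definitions in Protocol 17.8 and in the eCRF guidance:

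- *Related*: there is a reasonable possibility that the drug caused or contributed to the event, even if other causes may also have contributed.
- *Not related*: there is no reasonable possibility.

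Ask for the judgement separately for SCY-078/placebo and for voriconazole, as SAP 10.3 already presupposes.

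SAP Sections 11 and 12 say enrollment stopped at 22 subjects, so new wording alone may do little. Re-query causality for recorded AEs while assessors are still blinded, and finish before database lock, since SAP 3.7 unblinds the study team after lock. Keep the existing codes and report the drug-related AE summary under both codings. A re-query after unblinding could introduce bias of its own. If the database is already locked, disclose the limitation and rest the safety conclusions mainly on the all-cause tables.

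The cost is two sentences of protocol text, a small re-query for 22 subjects and one additional summary. The drug-related count may rise.
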